**PHASE 1: ATD Component Procedures.** Twenty-four participants will be included in the ATD component of this study. There are four discrete emotions (anger, sadness, anxiety, and guilt) under investigation and participants will be randomly assigned to complete study procedures for only one emotion. Six participants will be assigned to each emotion condition. Following usual and customary procedures for ATDs, the first participant for each discrete emotion will comprise the main experiment with the subsequent participants serving as replications. Each participant will be presented with six emotion inductions (focused on the emotion related to their assigned condition), occurring on six separate days over the course of two weeks. In order to maximize clinical relevance, emotional stimuli used in the emotion inductions will be tailored to each individual by instructing participants to write about a time in the past two months in which they felt the particular emotion being induced. This strategy has been successfully implemented previously by the PI to induce strong emotions in individuals with BPD. Prior research has suggested that using idiographic stimuli (vs. standardized stimuli) results in greater emotional reactivity in individuals with BPD and anxiety disorders. Prior to the first emotion induction in the first session, study staff will assist participants in developing a list of situations, occurring in the past two months, that brought up the emotion consistent with the condition to which the participant is assigned. Participants will be asked to rate the emotional intensity of each situation (on a 1-100 scale consistent with subjective units of distress) and six situations rated above 60 (to ensure sufficiently strong emotion is induced) will be chosen as the basis for the emotion induction writing assignments.

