Following each emotion induction, participants will be instructed to either act consistent or inconsistent with the emotion induced; instructions will be randomly alternated so that each participant will act consistent during 3 sessions and act inconsistent during 3 sessions. The randomization schedule will be such that one condition will not be presented more than two times in a row. Participants will be informed that “the goal of this project is to test out two different strategies for coping more effectively with emotions in order to ascertain the most effective strategy for you.” The two conditions will both be presented as credible and effective strategies to the participants in order to minimize any biased results due to expectancy effects. The specific instructions for acting inconsistent and consistent with EDBs following the mood induction will be based on idiosyncratic action urges associated with the induced emotions. For example, the guilt induction may elicit action urges to withdraw/hide and/or (albeit less commonly) lash out in an effort to deflect blame. Acting inconsistent to urges to withdraw may involve making plans with friends (via phone or email) or making small talk with confederates while acting inconsistent to urges to lash could include writing thank you notes to loved ones or engaging in an act of kindness. Study staff will assess for idiosyncratic emotion-driven action urges after the emotion induction to craft appropriate behavioral instructions relevant for the individual.

An important advantage of SCEDs is that the flexible nature of these studies and the immediate availability of results allows for the real-time alteration of procedures in order to obtain an effect on the putative mechanism of action. In this case, if we fail to find reductions in the intensity of the induced emotion by asking participants to act inconsistent with their reported action urges, we may, for example, extend the purview of behaviors to include emotion-consistent/inconsistent posture, and tone of voice. Making these changes informs the development of interventions by evaluating various strategies to manipulate putative mechanisms. The strategies tested can be confirmed by replication and also associated with individual characteristics. Participants will be paid \$40 per session for a total of \$240 for completing the entire six study sessions.

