**DATA ANALYSIS: PHASE I & II.** *Phase I Data Analyses:* Hypotheses regarding differential outcomes between the two strategies (acting consistent versus inconsistent) will be evaluated using a combination of classical methods of idiographic data-analysis and modern non-parametric statistical techniques. We will first plot parallel lines representing intensity of emotion as a function of each individual strategy. These will be directly compared as to changes in level and slope. In addition to customary visual observation (often, functions in ATDs yield non-overlapping datasets), more quantitative evaluations will also be employed by conducting non-parametric randomization and bootstrap tests of the mean differences between the two conditions. The non-parametric statistical analyses will be conducted using the Single-Case Randomization Tests package (SCRT) within the R statistical framework. Randomization tests will be conducted regarding levels of mean change in self-reported emotional intensity and clinician-rated facial emotional intensity from post-induction to post-regulation condition (acting consistent/inconsistent). Results from these non-parametric randomization tests will be used in conjunction with the visual observations for each individual to draw conclusions regarding the effect of acting counter to EDBs on the intensity of emotion relative to acting consistent with emotional urges.

*Phase I, Hypothesis 1:* When instructed to respond to induced emotions by acting inconsistent to emotional urges, participants will demonstrate greater reductions in the intensity of their emotions compared to acting consistent with their emotional urges. Similar patterns of results are expected across all discrete emotions induced.

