*Phase II Data Analyses:* The multiple baseline and phase change design will make between- and within-subjects analysis possible. By applying different baseline lengths across individuals, between-series comparisons will be possible to determine if changes in EDBs, emotional intensity, and emotional tolerance occur when and only when the intervention is applied. The phase change (baseline phase to treatment phase) process will allow for within-series comparisons to examine concomitant changes in EDBs, emotional intensity, and emotional tolerance when treatment is present compared to when it is absent within individuals. For both between-and within-subjects comparisons, we will first plot parallel lines representing changes in these variables over time for each individual. These will be directly compared in terms of changes in level and slope to determine if differences seen are due to phase change. We will also conduct non-parametric randomization tests of mean differences in EDBs, emotional intensity, and emotional tolerance as a function of phase using the SCRT within the R statistical framework. Results from these tests will be used with visual inspection of data to draw conclusions regarding effects of the intervention on frequency of EDBs, emotional intensity and emotional tolerance. We will also explore maintenance effects of our intervention by examining stability in EDBs, emotional intensity, and emotional tolerance during the follow-up phase. Finally, as an exploratory analysis, we will examine phase effects (baseline, treatment, follow-up) on clinician rated and self-reported BPD symptoms.

*Phase II, Hypothesis I:* Individuals will demonstrate change in self-reported frequency of EDBs, intensity of emotion (PANAS) and tolerance of emotions (MEAQ), as well as behavioral willingness to act inconsistent with emotional urges (PASAT-C) only after treatment is applied. *Phase II, Hypothesis II:* Change in these variables will be maintained during a 4-week follow up period. *Phase II, Hypothesis III:* In this exploratory analysis, we hypothesize that clinician-rated and self-reported BPD symptoms (ZAN-BPD, ZAN-BPD-srv) will decrease when and only when the intervention is applied, and only for patients who demonstrate reduction in EDBs.

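### Phase I draws conclusions for each participant from plots and a randomization test with no visual criterion, precedence rule or stated masking, and with three sessions per condition the individual test cannot reach 5%.

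*Combined protocol and SAP*

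**What the plan says.** Phase I Data Analyses (Combined protocol and SAP) plots, for each participant, one line of emotional intensity per strategy. Of these lines it says: "These will be directly compared as to changes in level and slope". The only visual pattern it mentions is that data sets in alternating treatment designs often do not overlap. Randomization and bootstrap tests of the mean difference follow, on self-reported and on facial intensity. The concluding sentence is: "Results from these non-parametric randomization tests will be used in conjunction with the visual observations for each individual to draw conclusions". No alpha, sidedness, visual threshold or order of precedence is given.

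The section PHASE 1: ATD Component Procedures fixes the amount of data: "instructions will be randomly alternated so that each participant will act consistent during 3 sessions and act inconsistent during 3 sessions". It also restricts the order: "The randomization schedule will be such that one condition will not be presented more than two times in a row". On numbers it says "Twenty-four participants will be included in the ATD component of this study" and "Six participants will be assigned to each emotion condition", and it treats the first participant for each emotion as the main experiment and the rest as replications.

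Whether those who read the Phase I plots know the condition labels is not stated. The only sentence on blinding concerns the Phase II evaluators. Phase II Data Analyses has a parallel sentence: "Results from these tests will be used with visual inspection of data to draw conclusions regarding effects of the intervention".

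**The concern.** Visual inspection carries weight only if it is known what the reader looks for and how often chance supplies it. The plan specifies neither, and three points per line give the eye little to work with. The test that should discipline the eye is itself limited at the individual level, because so few orders are allowed.

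If the test cannot reach a conventional level for one person, the words about combining the two sources do not say what happens next. Either no individual can be positive, or the plot settles it under a criterion nobody has written down. Hypothesis 1 depends on these individual verdicts, and the Timeline section plans a larger efficacy application after this project.

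**Working it through.** **Inputs.** Three sessions per condition, six in all; no condition more than twice in a row (both from PHASE 1: ATD Component Procedures); 24 participants, six per emotion (same section); direction from Phase I, Hypothesis 1. Assumptions: no effect, exchangeable sessions, no ties, every allowed order equally likely.

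**The plan's own figure.** It states no error rate for the plots or the individual test, so there is none to reproduce. The Power Analyses count of 18 observations per condition per emotion agrees with 6 × 3 = 18 and confirms three points per line. The stated total of 180 does not follow from 24 × 6 = 144; that is a separate matter and is not used here.

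**1. Chance separation in one participant.**
- Complete non-overlap, predicted direction: 1/C(6,3) = 1/20 = 5%. Either direction: 2/20 = 10%.
- First, second and third points, paired by order of occurrence, all in the predicted direction: (1/2)^3 = 1/8 = 12.5%. Either direction: 25%.

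Enumerating all 720 rank orders over the allowed sequences returns the same four values.

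**2. Expected number among 24, per index, predicted direction.**
- Non-overlap: 24 × 1/20 = 1.2.
- Paired points: 24 × 1/8 = 3.

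**3. Floor of the individual randomization test.** There are C(6,3) = 20 orders of three and three. Excluding those with a run of three or more leaves 14. Swapping the two labels turns any allowed order into another allowed order. Hence:
- smallest one-sided p = 1/14 = 0.071
- smallest two-sided p = 2/14 = 0.143

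Both exceed 0.05 whatever the data.

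**4. What combining participants does.** Two participants give 14 × 14 = 196 joint orders, so the smallest one-sided p is 1/196 = 0.005. A combined test can therefore reach 5% from two participants upward, and each emotion has six.

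**5. Precision of slope.** With session SD s, the SE of the difference between two fitted slopes is s × sqrt(1/Sxx_A + 1/Sxx_B), where Sxx is the sum of squared deviations of session number for a condition.
- Order ABBAAB: both Sxx = 8.67, SE = sqrt(2/8.67) = 0.48 s per session (smallest of the 14).
- Order AABABB: both Sxx = 4.67, SE = sqrt(2/4.67) = 0.65 s per session (largest).

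**6. Sensitivity to a session trend.** Six inductions in two weeks could show habituation. The documents give no trend size, so it was varied (normal noise, no effect, averaged over the 14 orders). The last column is the chance that at least 7 of 24 participants separate, the count needed for one-sided p below 0.05 if the rate were 1/8.

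| Trend per session | Paired-point separation | At least 7 of 24 |
|---|---|---|
| 0 | 12.5% | 2.4% |
| 0.25 SD | 13.6% | 3.6% |
| 0.5 SD | 16.3% | about 8% |
| 1 SD | 22.4% | about 28% |
| purely monotone | 4/14 = 28.6% | 55% |

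Non-overlap moves the other way. In a purely monotone series it would need an order such as AAABBB, which is not allowed, so its chance falls to zero. A fixed chance rate is unsafe for either criterion.

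**The case against.** Visual analysis is customary in single-case work, and the plan uses it jointly with a test. Joint use most naturally means that both sources bear on the conclusion. The design also builds in replication within each emotion and describes its indices as convergent. Even at 1 in 8, four or more of six participants in one emotion would separate by chance with probability (15 × 49 + 6 × 7 + 1)/8^6 = 778/262,144 = 0.3%. All of this stands, and it limits what can be claimed.

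A reader might infer four stronger things, and the documents support none of them.
- That the plots are read unmasked. The plan is silent. Results being available at once and staff devising the instructions make masking of session staff unlikely, but do not settle who reads the plots.
- That the plot is a second route, sufficient on its own. The plan does not say so.
- That one good-looking plot among 24 establishes an effect, so that the chance of at least one (71% for non-overlap, 96% for paired points) is the study's error rate. The plan has no such rule.
- That 1 in 8 is the plan's rate. It belongs to a pairing the plan never describes; the pattern the plan names gives 1 in 20.

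The objection does not remove the missing criterion and precedence rule, or the floor on the individual p-value. Replication guards against chance, but not against a criterion chosen after the plots are seen.

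**Conclusion.** The point holds for Phase I. Individual conclusions rest on plot and test together with no written criterion, no precedence and no stated masking. In the predicted direction, chance separation runs from 1 in 20 (the pattern the plan names) to 1 in 8 (paired points), or 1.2 to 3 of 24 participants per index. The floor on the individual test is exact given 14 equally likely orders. The inference that a positive individual verdict would rest largely on the plot assumes a 5% level, which the plan does not state. The bootstrap test might be offered as a further support, but the concluding sentence gives it no role.

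The separation rates assume exchangeable sessions without ties; trend or carry-over would change them. The parallel wording in Phase II might suggest the same figures apply there. They do not: the design differs, no Phase II rate has been derived, and the claim is limited to Phase I.

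**What to change.** In Phase I Data Analyses:

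1. Draw each participant's plot with the two conditions coded at random as X and Y. Fix the criterion beforehand, for example complete non-overlap in either direction, and record the verdict before decoding. Decoding then shows whether the direction is the predicted one.
2. Let Hypothesis 1 be decided by a randomization test combined across participants, per emotion and over all 24, drawing from the 14 allowed orders for each person. State the level and sidedness. Report individual p-values and plots as descriptive. Making the individual test decisive would not work, since at 5% it could never be positive.
3. If the number of separated plots is reported, compare it with its re-randomization distribution over the allowed orders, holding the observed scores fixed. Do not compare it with a fixed 3 of 24 or 7 of 24, because a session trend changes that rate.
4. Describe slope, but do not use it as a criterion.

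Masked reading is not proposed for Phase II, where the order of phases is visible in the plot.

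The cost is a few sentences and a few lines of plotting and test code, with no new data or staff. The downside is that isolated good-looking individual plots can no longer be called effects.

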**Study Population:** Participants will include 32 men and women who are at least 18 years of age. *Phase I* will include 24 participants meeting DSM diagnostic criteria for BPD (as determined by the DIPD, see Study Measures below) and *Phase II* will include 8 individuals diagnosed with BPD (per the DIPD); samples of this size are customary for SCEDs (see detailed description of power in the Data Analysis section below). Following long-standing procedures for clinical trials at CARD, participants in both phases who are on psychotropic medications will be included if they are willing to maintain a constant dosage throughout study sessions. This avoids problems with reluctance to discontinue or difficulty with discontinuing, and also the confounding of outcomes from initiation of medication during treatment. Because of the difficulty maintaining a consistent dose for PRN medications that are taken as needed per the patient's discretion, participants on PRN psychotropic medications will be excluded. Medication usage will be assessed weekly in order to control for any changes that may arise (described below). Additionally, participants in Phase II must also be willing to refrain from any additional psychosocial treatment during the course of the study and have their own smartphone.

*Exclusion criteria.* Exclusion criteria in this study provide the basis for determining whether participants are demonstrating lower-risk BPD symptoms. In order to maximize generalizability, exclusion criteria are based solely on the well-being of the participant and will consist primarily of conditions that would require prioritization for immediate treatment (e.g., severe suicidality or substance dependence). Specifically, these conditions include: (a) current *DSM-5* diagnoses of bipolar disorder, schizophrenia, schizoaffective disorder, or organic mental disorder; (b) clear and current suicidal risk (intent) and (c) current or recent (within 3 months) history of drug dependence. Individuals will also be excluded if their emotional symptoms are due to a medical/physical condition in which case alternative treatment would be clinically indicated.

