*Patient flow and feasibility.* Participants will primarily be recruited from local treatment sites currently reporting an overflow of BPD patients; these include the intake and referral offices at Massachusetts General Hospital and the McLean Hospital (see letters of support from clinical faculty at these institutions in Other Attachments). Additionally, participants will be recruited through CARD's general client population. CARD completes over 1000 new patient screenings per year of which approximately 15% endorse symptoms of BPD; rather than refer these individuals out for BPD treatment elsewhere, they will be sent to this study for further assessment. Finally, we will also advertise specifically for the study in locations and publications commonly advertising treatment studies. These recruitment procedures are consistent with a recent data collection at CARD that enrolled 50 individuals with BPD (and comorbid Bulimia Nervosa) over the course of 4 years in the context of an NIMH-funded Career Development Award (PI: [name]). Further, while recruiting for a small pilot study, 4 patients meeting the current study's eligibility criteria were recruited from the above sources in a two-month period (2 from CARD, 1 from McLean Hospital, and 1 from Massachusetts General Hospital). Recruitment at this rate during the proposed project would be sufficient to achieve enrollment goals.

*Participant Retention:* In both phases, participants that discontinue will be replaced. However, we will employ procedures during both study phases to reduce potential dropout. First, at the baseline assessment, the PI will personally meet with participants to provide them with a plan for discussing any concerns as they arise throughout the study. Specifically, participants will be informed that they should first address concerns directly with study staff (IEs) or the PI. In cases where patients may not feel comfortable addressing the PI directly, [name] (the mentor on this study and Director Emeritus of the clinic) may be involved to resolve concerns with patients. This will establish a positive working alliance with the research "team." Additionally, study staff will be flexible in re-scheduling missed sessions within reasonable limits. These procedures recommended by Marsha Linehan and others involved in treating patients with BPD and co-occurring disorders and will be overseen by [name], a close collaborator on this project with

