*Power Analyses.* Sample size in SCEDs refers to the number of observations collected. In Phase I, 35 observations (ratings of emotional intensity) will be collected for each emotion under study (18 acting consistent with emotional urges and 18 acting inconsistent); this will yield 180 total observations with 90 in each condition. Phase II will result in 88 observations for weekly measures and 616 observations for daily

measures. These numbers of observation will make possible detection of medium effect sizes across both phases.

**Timeline Timetable:** Support is requested for 4 years in order to successfully complete both phases of the project, which are integral to the applicant's training goal to gain expertise in exploring mechanisms of action in treatment. Year 1 of the project will be dedicated to acquiring advanced training in the assessment of physiological and behavioral indicators of emotion to corroborate self-report data and for training study staff. Recruitment and data collection for Phase I will take place in Year 2. Recruitment and data collection for Phase II will begin in the 9th month of Year 2 and continue through Year 3. Additionally, in Year 3, data analyses will be started and an R01 application for a larger-scale efficacy trial examining the effect of countering EDBs on BPD symptoms will be submitted. A larger N will make possible longitudinal repeated-measurement of treatment mediators and exploration of moderators (e.g., severity). Finally, Year 4 will be used to complete data analyses, prepare manuscripts, and re-submit the R01 application.

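### The Phase I observation counts in the power paragraph do not follow from the design: it yields 36 per emotion, 144 in total and 72 per condition, not 35, 180 and 90

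*Combined protocol and SAP*

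**What the plan says.** The Power Analyses paragraph (combined protocol and SAP, at the end of Data Analysis: Phase I & II) opens with its unit: "Sample size in SCEDs refers to the number of observations collected". For Phase I it then states "35 observations (ratings of emotional intensity) will be collected for each emotion under study (18 acting consistent with emotional urges and 18 acting inconsistent", and concludes that "this will yield 180 total observations with 90 in each condition". After the Phase II counts comes its only statement about power: "These numbers of observation will make possible detection of medium effect sizes across both phases". It gives no significance level, power target or numerical effect size.

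The design is set out in PHASE 1: ATD Component Procedures: "Twenty-four participants will be included in the ATD component of this study", each assigned to one of four emotions, and "Six participants will be assigned to each emotion condition". Each participant has six inductions on separate days, three followed by each instruction.

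Two other places bear on the count. Study Population supports the numbers enrolled by saying that "samples of this size are customary for SCEDs (see detailed description of power in the Data Analysis section below". Participant Retention says that "In both phases, participants that discontinue will be replaced".

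**The concern.** The Phase I sentence disagrees with itself and with the design. Its two parts per emotion do not add up to its total per emotion, and neither figure, multiplied by four emotions, gives the overall total.

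The paragraph makes the number of observations the sample size, and Study Population sends the reader to it for the justification. So 180 is in effect the stated Phase I sample size, and the medium-effect conclusion is drawn from it. A reader who relies on the paragraph would credit Phase I with a quarter more data than it will collect.

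**Working it through.** **Inputs** (PHASE 1: ATD Component Procedures): 24 participants; four emotions; one emotion per participant; six participants per emotion; six sessions per participant; three sessions per condition.

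**The plan's own figures.** 18 + 18 = 36, not 35. Over four emotions, 4 × 35 = 140 and 4 × 36 = 144; neither is 180.

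**Counts from the design, one observation per session.**

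| Count | Arithmetic | Design | Stated |
|---|---|---|---|
| Per emotion | 6 × 6 | 36 | 35 |
| Per emotion and condition | 6 × 3 | 18 | 18 |
| Total | 24 × 6 | 144 | 180 |
| Per condition | 24 × 3 | 72 | 90 |

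180/144 = 90/72 = 1.25, an overstatement of 25%.

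**Other ways of reaching 180.** Two ratings, or two measures, per session: 144 × 2 = 288. All 32 participants of both phases: 32 × 6 = 192. Five emotions at 35: 175. The figure of 180 appears only as 5 × 36 (five emotions) or 30 × 6 (30 participants), with 5 × 18 = 90 to match. Neither is in the plan.

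**Is one observation per session the right unit?** The stated 18 per condition is 6 participants × 3 sessions, so the sentence itself counts each session once. Phase II follows the same kind of rule. Assuming four participants on each baseline length, with four weeks of intervention and four of follow-up, 4 × (2 + 4 + 4) + 4 × (4 + 4 + 4) = 88 weeks, and 88 × 7 = 616 days. Both match the paragraph. Phase I Data Analyses also tests one change per session, from after the induction to after the instructed behaviour.

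**Effect on the medium-effect sentence.** The inputs here are assumptions: d = 0.5 in units of the total SD, two-sided 5%, the same effect in everyone, normal approximation, and correlation ρ between one participant's sessions.

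SE = √(2(1 − ρ)/n), and power = Φ(d/SE − 1.96), with n observations per condition.

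At ρ = 0:
- n = 90: SE = 0.149, 0.5/0.149 = 3.35, Φ(1.39) = 0.918
- n = 72: SE = 0.167, 0.5/0.167 = 3.00, Φ(1.04) = 0.851
- n = 18 (one emotion): SE = 0.333, 0.5/0.333 = 1.50, Φ(−0.46) = 0.323

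| n per condition | ρ = 0 | ρ = 0.3 | ρ = 0.5 |
|---|---|---|---|
| 90 | 92% | 98% | nearly 100% |
| 72 | 85% | 95% | 99% |
| 18 | 32% | 43% | 56% |

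At ρ = 0 the difference detectable with 80% power is 2.80 × SE: 0.47 SD with 72 per condition and 0.42 SD with 90.

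**If the effect varies between participants.** Take the 24 within-participant differences between means of three sessions, with SD τ for the participants' true effects: SE = √((2(1 − ρ)/3 + τ²)/24), using a paired t-test on 23 degrees of freedom. For ρ from 0 to 0.5, power is 82% to 98% with τ = 0, and 69% to 87% with τ = 0.5. If medium instead means half an SD of the 24 participant differences, power is 65%. With 30 participants, which is what 180 implies, the case τ = 0.5 and ρ = 0 gives 79%, so variation between participants matters with either count.

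**The case against.** The best defence is that nothing depends on 180 or 90. Enrolment, randomisation, payment and analysis all follow from 24 participants and six sessions, which the plan states consistently. Study Population gives custom in single-case designs as its first reason for the sample, and the 24 stated there is correct. This stands, and it limits the point to the sample size justification. It does not make the figures right, because the paragraph itself equates sample size with observations and argues from those numbers.

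An allowance for dropout might be offered to explain 30 participants. The replacement rule leaves no need for one. The plan does not say whether partial data from replaced participants are kept, but such data would be an unplanned extra and not a fixed total of 180.

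It might also be noted that the Study Overview lists shame where the Phase 1 procedures list guilt, so five emotions are named across the text. Each list has exactly four, and four groups of six account for all 24 participants.

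Two stronger readings are tempting. One is that the correction leaves Phase I underpowered; the other is that the medium-effect claim plainly survives it. The documents support neither, since they give no effect size, error rate or correlation. Phase I Data Analyses reads its tests together with plots for each individual and describes no test pooled over participants. Nor do the documents show that Phase I is six participants short, or that a fifth emotion was dropped.

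**Conclusion.** The counts are wrong as written. This rests only on the plan's own design figures and on its own convention of one observation per session; no reading of a four-emotion, 24-participant design that was tried gives 180 and 90.

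What the correction does to the medium-effect sentence is conditional. A pooled comparison would stay above 80% under the favourable assumptions shown (85% at ρ = 0 with a common effect). It could fall below 80% if participants respond differently, and the statement would not hold for a single emotion at ρ = 0 (32%). Which of these applies cannot be settled until the plan names the analysis that the sentence covers.

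Severity is minor: the error is certain and sits in the only quantitative sample size justification, but it changes nothing that will be done.

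**What to change.** In Power Analyses, restate the Phase I counts as 36 observations per emotion (18 for each instruction), 144 overall and 72 per condition, and say that each session contributes one observation. Defining that observation as the change from after the induction to after the instructed behaviour would match Phase I Data Analyses.

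Then re-check the medium-effect sentence against 144 and 72, state the effect size and error rates assumed, and name the analysis it refers to: individual, within emotion or pooled. If a pooled test is meant, Phase I Data Analyses must also say how participants are combined. The count correction does not wait on that.

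The cost is wording and a short recalculation, with no added participants, sessions or measures.
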